Title of Study: A Multicenter, Randomized, Double-Blind, Parallel Group, Placebo-Controlled Study to Compare the Efficacy and Safety of High-medium Molecular Weight Beta-Glucan in Subjects with Hyperlipidemia with or without Statin Therapy.		
Principal Investigator: [name]		
Study Sites: Up to twelve (12) study sites in Canada		
Treatment duration: 12 weeks	Phase of Development: 2	
Objective: The objective of this study is to evaluate the effects of beta-glucan (1.5 g, 3 g or 6 g daily) administered three times a day (TID) in divided doses on heart disease lipid risk factors.		
Methodology: Male and female subjects \geq 18 years of age with an elevated LDL-C $>$ 3.37 mmol/L (130 mg/dL) treated with a stable dose of statin for at least 6 weeks or not treated with a statin. Following signature of informed consent, approximately 264 subjects (66 subjects per beta-glucan treatment group and 22 subjects per matching placebo group) meeting all inclusion criteria and no exclusion criteria will be randomized to receive one of the three doses of beta-glucan (1.5 g, 3 g or 6 g daily) administered TID in divided doses or a matching placebo. The subjects will be assigned to the 3 different doses of beta-glucan or placebo in a tiered fashion as follows: 
• The first set of 88 subjects randomized will receive either 1.5 g beta-glucan daily (1 tablet of 500 mg TID) or a matching placebo in a 3:1 ratio,• The next set of 88 subjects randomized will receive either 3 g of beta-glucan daily (2 tablets of 500 mg TID) or a matching placebo in a 3:1 ratio,• The last set of 88 subjects randomized will receive either 6 g of beta-glucan daily (4 tablets of 500 mg TID) or a matching placebo in a 3:1 ratio. During the treatment period, subjects will return to the study site at Visit 3 (Week 6) and at the End of Treatment Visit (Week 12) for laboratory tests and clinical assessments, including Adverse Events (AEs), dietary guidance and study product compliance. At the Safety Follow-up Visit (Week 14), subjects will be contacted via telephone for an assessment of AEs.		
Number of Subjects: Planned: Approximately 310 subjects screened to randomize approximately 264 subjects (66 per treatment group and 22 per matching placebo group).		
Diagnosis and Main Criteria for Inclusion: Male and female subjects \geq 18 years of age with an elevated LDL-C $>$ 3.37 mmol/L (130 mg/dL) treated with a stable dose of statin for at least 6 weeks or not treated with a statin.		
Test Product, Dose/Strength/Concentration, Mode of Administration: Test product: Oat beta-glucan tablet is a natural health product of high-medium molecular weight produced through CEAPRO's proprietary and patented Pressurized Gas eXpanded technology. Dose: 1.5 g or 3 g or 6 g daily Mode of administration: oral		

Duration of Treatment:

Twelve weeks of treatment with beta-glucan 1.5 g, beta-glucan 3 g, beta-glucan 6 g (total daily dose) or a matching placebo.

Each subject is expected to participate for about 15 weeks (up to 1 week of screening, 12-weeks of treatment and follow-up call 2 weeks after last dose taken).

Criteria for Evaluation:

Efficacy:

The primary efficacy endpoint will be the change from Week 0 to Week 12 in direct-measured LDL-C.

The secondary efficacy endpoints will be changes from Week 0 to Week 12 in total cholesterol (TC), non-High-density lipoprotein cholesterol (non-HDL-C), small low-density lipoprotein (LDL) subclass particle concentration, high sensitivity C-reactive protein (hsCRP), very low-density lipoprotein cholesterol (VLDL-C), and apo B.

Exploratory endpoints will include changes in HDL-C, triglycerides, Lipoprotein (a) (Lp(a)) and glycated hemoglobin (HbA1c).

Safety:

Safety will be assessed by adverse events, physical examination, vital signs, ECG, and laboratory analyses (hematology, biochemistry).

Statistical Methods:

Sample Size:

Sample size computation is based on the change in LDL-C. Based on previous literature, we are expecting a mean decrease from baseline to follow-up in LDL-C of 0.30 mmol/L (11.6 mg/dL) in the control group and we are aiming to show that the addition of beta-glucan, either at 1.5 g, 3 g or 6 g, will further reduce LDL-C by 0.30 mmol/L, leading to an expected difference in change in LDL-C of 0.30 mmol/L between the control group and at least one of the active groups. The expected standard deviation of the change in LDL-C is 0.50 mmol/L (19.3 mg/dL). To reach a power of 80% in detecting this 0.30 mmol/L difference with a two-tailed significance level of 0.0167 (to account for the three main comparisons: placebo vs. beta-glucan 1.5 g, placebo vs. beta-glucan 3 g and placebo vs. beta-glucan 6 g), 60 subjects per group are required for a total of 240 subjects. To account for approximately 9% lost to follow-up, 264 subjects (66 subjects per treatment group) will be randomized.

Efficacy:

The primary dataset for efficacy analyses will be the set of all randomized subjects (ITT Population).

For the primary, secondary and exploratory endpoints, the values at each study visit and the changes from Week 0 to follow-up visits (week 6 and week 12) will be summarized for each treatment group using descriptive statistics. The changes will be compared between treatment groups using repeated measures analysis of covariance (ANCOVA) models adjusting for the Week 0 value. Contrasts under these models will allow for the three main comparisons: placebo vs. beta-glucan 1.5 g, placebo vs. beta-glucan 3 g and placebo vs. beta-glucan 6 g. For the primary endpoint, these comparisons will be done at the 0.0167 significance level. The significance level will be set to 0.05 for all other analyses.

Safety:

The primary dataset for safety analyses will be the set of all randomized subjects who received at least one dose of investigational product (IP) (Safety Population).

Adverse events will be coded using the Medical Dictionary for Regulatory Affairs (MedDRA) coding dictionary. Treatment-emergent adverse events will be summarized for each treatment group.

Treatment-emergent adverse events will be defined as adverse events with a start date on or after the first dose of study product.

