6.2 Randomization and Treatment Procedures

Urine pregnancy test is repeated in females of childbearing potential at the randomization Visit 2.

Subjects considered by the investigator to meet all entry criteria are scheduled for randomization at Week 0 (Visit 2) where subject receives either CP105F (1.5 g, 3 g or 6 g) or matching placebo in a double-blinded fashion. Dietary counselling per Appendix 1, and IP and statin (for subjects who are taking statins) administration instructions are reviewed with the subject at each dispensing visit (Visits 2 and 3), and IP and statin (for subjects who are taking statins) compliance is assessed at subsequent visits (Visits 3 and 4):

- IP administration: 1, 2 or 4 tablets (based on the dosing arm currently recruiting) taken TID in the morning before breakfast, at mid-day before lunch and before supper time preferably at the same times every day. Subjects should be clearly instructed that if a dose is missed, the next regularly scheduled dose should be taken and unused tablets returned at the next study visit.
- Statin administration (for subjects who are taking statins): in the evening or least 2 hours after the last dose of IP.

During the 12-week treatment period, visits will take place at Weeks 6 and 12 (Visit 3 and 4 respectively, \pm 5 days), followed by a Safety Follow up (Visit 5, \pm 5 days) at Week 14.

Subjects will continue to receive dietary counselling throughout the course of the treatment period and have labs measured as outlined in Appendices 2 and 3. Subjects will be assessed for compliance to IP through pill counts (see section 5.3). At each visit, subjects will be questioned in a non-specific manner for the occurrence of Adverse Events.

Safety assessments may be done at any time during the subject's participation in the study. Follow-up phone call will be performed 2 weeks after last dose taken for capturing any AEs.

6.3 Medical History:

Medical History will consist of detailed information, with particular attention to identify factors that would exclude a patient, including: age, race, sex, current medications, drug sensitivities or any adverse reactions to medications, history of hepatic, renal, or cardiovascular disease,

smoking history, alcohol intake, drug abuse, prior hospitalizations, surgeries, interventions, and serious illnesses

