6.2 Statistical Considerations

This is a randomized, parallel study with four treatment groups (placebo, beta-glucan 1.5 g, beta-glucan 3 g and beta-glucan 6 g). The statistical analysis will focus on the comparisons of the three active groups vs. placebo.

Descriptive statistics of all study variables will be presented overall and broken down by treatment group. Number of observations, mean, standard deviation, median, minimum and maximum will be presented for continuous variables. Count and proportion will be displayed for categorical variables.

Basic assumptions of the proposed analyses will be checked and data transformation or other analyses could be done if appropriate. For example, as some endpoints are likely to be skewed (ex. triglycerides, hsCRP), log-transformation might be used, in which case descriptive statistics would also include geometric means.

Laboratory parameters will be assigned to visits based on number of days from randomization and not based on scheduled visit at which the measurement was made. The time windows that will be used to assign measurements to visits are given in Appendix 2.

Values entered as less than a specified value will be considered as the specified value divided by 2 (e.g. entered value <0.2 will be analyzed as 0.1). Values entered as BLQ (Below Limit of Quantification) will be considered as the limit of quantification divided by 2. Values entered as more than a specified value will be considered as the specified value.

All statistical tests will be two-sided. Tests involving the comparisons of the active groups vs. placebo for the primary endpoint will be conducted at the 0.0167 significance level. All other tests will be considered secondary or exploratory and will be conducted at the 0.05 significance level.

No interim analysis on efficacy endpoints is planned for this study.

Statistical analyses will be done using SAS version 9.4 or higher.

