6.3.6 Treatment Compliance

An overall compliance calculation will be performed using primarily the study administration intake recorded on the Drug Accountability Form of the eCRF or on the Investigational Product Use Form of the eCRF if information regarding study medication returned/lost is missing. Compliance for the whole study is derived as follows:

| | | |
|------------------------|-----------------------|---|
| | Pill counts (%) | $\frac{[\text{sum of caplets dispensed} - \text{sum of caplets returned} - \text{sum of caplets lost}] \times 100}{[\# \text{ caplets to take per day} \times (\text{date last scheduled visit} - \text{date rando})]}$ |
| Compliance overall (%) | Days on treatment (%) | 
If # of caplets dispensed ≠ missing AND If information regarding study medication returned is missing (i.e. # of caplets returned is missing and/or # of caplets lost is missing)
 $\frac{[\text{date of last dose} - \text{date of first dose}] \times 100}{[\text{date last scheduled visit} - \text{date rando}]}$ |
| | NA | 
If # of caplets dispensed = missing OR If last scheduled visit = baseline
 |

Where

- Cohort 1 (rando number 001 à 280): Number of tablets dispensed = 147 (# caplets per day = 3)
- Cohort 2 (rando number 281 à 563): Number of tablets dispensed = 294 (# caplets per day = 6)
- Cohort 3 (rando number 564 à 997): Number of tablets dispensed = 588 (# caplets per day = 12)

Compliance will also be categorized as follow: < 80%, [80%-120%] or >120% and summarized accordingly using frequencies and percentages, by treatment arm, for the subjects of the ITT population.

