6.5.2 Adverse Events and Serious Adverse Events

6.5.2.1 Adverse Events

AEs will be coded by system organ class and body system according to the MedDRA dictionary (version 22.0).

The total number of TEAEs reported, the number and proportion of subjects experiencing at least one TEAE, at least one severe TEAE, at least one TEAE related to the study treatment, and at least one TEAE leading to drug withdrawal will be presented. In addition, number and proportion of subjects experiencing a treatment-emergent AE will be presented by system organ class and preferred term overall and for each treatment group.

A treatment-emergent AE will be defined as an AE with onset date on or after the date of first dose. If it is not possible to assess the timing of the start of the AE to the date of first dose due to incomplete AE onset date and/or incomplete date of first dose, the event will be assumed to be treatment-emergent.

All AEs will be listed but only treatment-emergent AEs will be summarized.

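### Placebo subjects take 3, 6 or 12 tablets a day by cohort, but the compliance, exposure and adverse event summaries use one pooled placebo group; add placebo columns by cohort

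*Protocol*

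**What the plan says.** **Allocation.** The protocol synopsis, Protocol 3.1 and SAP 2.1 describe three successive sets of 88 subjects. Each set is randomized 3:1 to one dose or its matching placebo: "66 subjects per beta-glucan treatment group and 22 subjects per matching placebo group".

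**Tablet count.** Protocol 6.2 ties the count to the set being recruited: "IP administration: 1, 2 or 4 tablets (based on the dosing arm currently recruiting) taken TID". SAP 6.3.6 gives the daily count for each whole cohort, active and placebo together, identified by randomization-number range: "Number of tablets dispensed = 147 (# caplets per day = 3" for cohort 1, "Number of tablets dispensed = 294 (# caplets per day = 6" for cohort 2 and "Number of tablets dispensed = 588 (# caplets per day = 12" for cohort 3.

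**Reporting groups.** SAP 6.2, like Protocol 10.2, describes the study as having "four treatment groups (placebo, beta-glucan 1.5 g, beta-glucan 3 g and beta-glucan 6 g"), with one placebo group. SAP 6.5.2.1 says that subjects with treatment-emergent events "will be presented by system organ class and preferred term overall and for each treatment group". SAP 6.5.1 treats exposure and discontinuation the same way, SAP 6.5.2.2 follows the adverse event format for serious events, and SAP 6.3.6 summarizes compliance by arm. No title in the SAP section 7 table list mentions a split of placebo by cohort. Safety is descriptive, without formal tests (Protocol 10.4, SAP 6.5).

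**The concern.** The pooled placebo group is not the randomized comparator of any one dose. For each dose, one third of it was randomized alongside that dose at the same tablet count. The other two thirds came from other cohorts and took a different number of tablets.

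The number of tablets can plausibly affect how many complaints are reported, how many subjects stop and how many doses are missed, whatever the tablets contain. If so, a comparison with pooled placebo mixes the effect of the product with the effect of tablet count, in opposite directions at the two ends of the dose range.

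The safety profile is a secondary objective (Protocol 2.2), and Protocol section 1 gives the need to define the dosage of the new formulation as a reason for the trial. Tolerability is a listed ground for stopping product (Protocol 5.5). Compliance of 80%, or 70% in the modified set, decides membership of the per-protocol sets (SAP 3.2 and 6.4.4.1). With no formal safety tests, readers will rely on the displayed percentages alone.

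**Working it through.** **1. The plan's own figures.** Three sets of 66 + 22 give 3 x 88 = 264, and 3 x 22 = 66 placebo subjects. The stated sample size (difference 0.30 mmol/L, SD 0.50 mmol/L, two-sided 0.0167, power 80%) reproduces: a noncentral t calculation gives 79.5% power at 59 per group and 80.3% at 60. Inflating for 9% loss, 60 / 0.91 = 65.9, so 66. The placebo group reaches 66 only by pooling the three cohorts. That pooling serves the LDL-C comparison, which this point leaves alone.

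**2. Tablet load.** Daily counts are 3 x 1 = 3, 3 x 2 = 6 and 3 x 4 = 12. With equal placebo cohorts the pooled mean is (3 + 6 + 12) / 3 = 7. Active minus pooled placebo is 3 - 7 = -4 at 1.5 g, 6 - 7 = -1 at 3 g and 12 - 7 = +5 at 6 g.

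**3. Effect on a displayed difference.** The documents give no event rates by tablet count, so the rest is assumption. Suppose that each daily tablet adds b percentage points to an event rate, equally for active and placebo tablets, and that beta-glucan adds nothing. The expected difference from pooled placebo is b x (tablets - 7), that is -4b, -b and +5b. Against the same-cohort placebo it is 0 throughout. The last column gives a true +8-point effect at 1.5 g as it would be displayed, 8 - 4b.

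| b (points per daily tablet) | 1.5 g | 3 g | 6 g | True +8 at 1.5 g appears as |
|---|---|---|---|---|
| 0 | 0 | 0 | 0 | +8 |
| 0.5 | -2 | -0.5 | +2.5 | +6 |
| 1 | -4 | -1 | +5 | +4 |
| 2 | -8 | -2 | +10 | 0 |
| 3 | -12 | -3 | +15 | -4 |

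**4. The same without a straight line.** Assumed rates of 10%, 15% and 25% at 3, 6 and 12 tablets give a pooled placebo rate of 50 / 3 = 16.7% and differences of -6.7, -1.7 and +8.3 points. Rates of 10%, 12% and 16% give 38 / 3 = 12.7% and -2.7, -0.7 and +3.3 points.

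**5. Precision of a cohort column.** One event in 22 is 1 / 22 = 4.5 points. At a 20% rate in both groups, the 95% half-width of a difference is 1.96 x sqrt(0.2 x 0.8 x (1/66 + 1/66)) = 13.6 points for 66 against 66, and 1.96 x sqrt(0.2 x 0.8 x (1/66 + 1/22)) = 19.3 points for 66 against 22.

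**The case against.** The strongest case against is that nothing in the documents shows any effect of tablet load, so the size is hypothetical; that the tables are descriptive; and that a column of 22 is noisier than most of the distortions it would reveal. In the assumed examples of 10/15/25% and 10/12/16%, the shifts at 6 g (+8.3 and +3.3 points) lie inside the 19.3-point half-width, and the smaller is less than one event in 22. This stands. It limits what the cohort columns can prove and is the reason to keep the pooled column.

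Three further objections also stand:
- Compliance percentages are already divided by each cohort's daily count (SAP 6.3.6). What remains is a possible difference in adherence behaviour between 3 and 12 tablets a day.
- All adverse events are to be listed (SAP 6.5.2.1, Listing 5), and cohort can be derived from the randomization number. The matched comparison could therefore be rebuilt for events; it is simply not planned as a summary.
- The SAP gives table titles without layouts, so a single placebo column is inferred, though strongly, from the four-group definition.

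A reader might infer more than the documents support:
- *That pooling creates a dose gradient.* It does not. Dose and tablet count rise together in the active arms by design, and subtracting one constant leaves their spread unchanged: 8.3 - (-6.7) = 15 = 25 - 10. Pooling only fails to remove the tablet-count part.
- *That mannitol or liquid volume is the mechanism.* Protocol 5.1.2 lists mannitol for the placebo tablet only, and Protocol 5.1.5 does not scale the liquid to the number of tablets.
- *That tolerability should be read only against the same-cohort placebo.* Matching on count does not guarantee equal non-drug effects per tablet. If placebo rates were 10%, 15% and 25% and every active arm had 10%, pooled placebo would give -6.7 points at each dose, while the matched columns would give 0, -5 and -15, an apparent benefit rising with dose.

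**Conclusion.** The point holds as a reporting gap. The trial randomizes each dose against a placebo with the same tablet count, and the planned summaries of compliance, exposure, discontinuation and adverse events do not show that comparison. If events or stopping rise, or adherence falls, with tablet count, the 6 g difference from pooled placebo is exaggerated and a true adverse effect at 1.5 g can be masked.

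The direction follows from the tablet counts, given equal placebo cohorts and a similar per-tablet effect in active and placebo. The size is unknown because the documents give no rates. Over the assumed range of 0 to 3 points per daily tablet, the shift is 0 to +15 points at 6 g and 0 to -12 at 1.5 g. No primary or secondary efficacy test is affected by this point. It should be corrected because the remedy is nearly free and concerns a stated secondary objective.

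**What to change.** In SAP 6.3.6, 6.5.1, 6.5.2.1 and 6.5.2.2, and in Tables 1.4.1, 3.1.1, 3.1.2 and 3.2.1 to 3.2.4:

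- Add placebo columns by cohort (3, 6 and 12 tablets a day, about 22 subjects each), each beside the active group randomized with it. Keep the pooled placebo column.
- Add a note saying that the within-cohort columns are the randomized, tablet-matched comparison; that they are imprecise, one event being about 4.5 points; and that any apparent dose gradient against pooled placebo should be checked against them.

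The cost is three extra columns in seven tables. Cohort is already defined by randomization number in SAP 6.3.6, so no new data, tests or design changes are needed. The drawback is that small columns invite over-reading, which the note is meant to limit.

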• EFSA	• European Food Safety Authority
• eCRF	• Electronic case report form(s)
• ES	• Evidence Statement
• ESC	• European Society of Cardiology
• EtOH	• Ethyl alcohol or alcohol
• FDA	• Food and Drug Administration
• G	• Gram
• GCP	• Good Clinical Practice
• GFR	• Glomerular filtration rate
• HbA1c	• Hemoglobin A1C, glycated hemoglobin or glycosylated hemoglobin
• Hb	• Hemoglobin
• HDL-C	• High-density lipoprotein cholesterol
• HMG-CoA	• 3-hydroxy-3-methyl-glutaryl-co-enzyme A
• hsCRP	• High sensitivity C-reactive protein
• ICF	• Information and Consent Form
• ICH	• International Council for Harmonisation
• IEC	• Independent Ethics Committee
• IDL-C	• Intermediate-density lipoprotein cholesterol
• IP	• Investigational Product
• IRB	• Institutional Review Board
• ITT	• Intention to Treat
• Kg	• Kilogram
• LDL-C	• Low density lipoprotein-cholesterol
• LOE	• Level of Evidence
• LP(a)	• Lipoprotein (a)
• MedDRA	• Medical Dictionary for Regulatory Activity
• Mg	• Milligram
• MHI	• Montreal Heart Institute
• MHICC	• Montreal Health Innovations Coordinating Center
• NCEP	• National Cholesterol Education Program
• NHLBI	• National Heart, Lung and Blood Institute
• Non-HDL-C	• Non-High-density lipoprotein cholesterol
• NYHA	• New York Heart Association
• PGX	• Pressurized Gas Expanded

GLOSSARY OF ABBREVIATIONS

• PCI	• Percutaneous coronary intervention
• SAE	• Serious Adverse Event
• SAP	• Statistical analysis plan
• SC	• Steering committee
• SUSAR	• Suspected unexpected serious adverse reaction
• TC	• Total cholesterol
• TDD	• Total daily dose
• TIA	• Transient ischemic attack
• TID	• Three times a day
• TLC	• Therapeutic Lifestyle Changes
• TG	• Triglycerides
• ULN	• Upper limit of normal
• USDA	• US Department of Agriculture
• VLDL-C	• Very low-density lipoprotein cholesterol
• WBC	• White blood cell

1 BACKGROUND AND RATIONALE

Hyperlipidemia is a potent risk factor for atherosclerosis and, implicitly for Cardiovascular Disease (CVD). CVD is one of the leading causes of death and disability in Canada and worldwide. Atherosclerotic coronary artery disease (CAD), the most common form of CVD, is characterised by plaque build-up inside the arteries. The plaque, or atheroma, is formed of fatty deposits, calcium and cells. The fatty deposits thicken the arteries and promote the accumulation of calcium and cells, leading to the formation of plaques. The plaque can then rupture diminishing the downstream blood flow by the formation of superimposed luminal thrombosis, which leads to either a heart attack or stroke depending on the artery affected. ^(1, 2, 3)

Lipid-related risk factors for atherosclerotic CAD include elevated levels of total cholesterol (TC), non-HDL cholesterol, very low-density lipoprotein cholesterol (VLDL-C), low-density lipoprotein cholesterol (LDL-C), apolipoprotein B (apo B or B-100), intermediate-density lipoprotein cholesterol (IDL-C), lipoprotein(a) and reduced concentrations of high-density lipoprotein cholesterol (HDL-C). ^(4,5,6)

LDL-Cholesterol makes up to 60-70% of the total serum cholesterol and the LDL particle has been identified as being the major atherosclerotic lipoprotein. The studies across different populations have shown that there is a positive relationship between serum LDL-C levels and the development of the first or subsequent attacks of Coronary Heart Diseases (CHD). ⁽⁴⁾

LDL-Cholesterol is the primary target of treatment in clinical lipid management. The therapeutic goal is achieved in many persons by using therapeutic lifestyle changes (TLC), including LDL-lowering dietary options (plant stanols/sterols and increased viscous fibre). Lifestyle changes include smoking cessation, an overall healthy eating pattern, with maintenance of appropriate body weight, and controlled blood pressure and diabetes. Nonetheless, the LDL-C goal currently often requires LDL-lowering drugs in patients at risk for CHD. ⁽⁴⁾ Clinical lipid management consists predominantly of HMG-CoA reductase inhibitors (statins), but also includes non-statin therapies such as bile acid sequestrants, ezetimibe and soluble/viscous fibre. ^(4, 7)

Non-HDL-Cholesterol and apo B are considered alternate therapeutic targets. Ho *et al.* have shown in a systematic review that there is a high correlation between CVD risk and both Non-HDL-C and apo B. ⁽⁸⁾

The regulatory agencies US Food and Drug Administration (FDA), Health Canada and European Food Safety Authority (EFSA) Panel on Dietetic Products, Nutrition and Allergies, approved claims for soluble fibre, as part of a diet low in saturated fat and cholesterol. ^(5, 9, 10)

Soluble/viscous fibre is found in whole oat food (oat bran, rolled oats, whole oat flour) and in barley foods. The National Cholesterol Education Program (NCEP) Expert Panel recommends, as part of the TLC, that the diet be enriched by foods containing at least 5–10 grams of viscous fiber daily. Intakes of 10–25 grams per day can be beneficial, being one of the therapeutic options for lowering LDL-C. ⁽⁴⁾ According to an ACC Expert Consensus, the mean TC and LDL-C levels were decreased relative to control by 9.7 and 11.6 mg/dL respectively with an intake of 3.0–12.4 g/day. ⁽⁷⁾ European guidelines for the management of

dyslipidemia notes that a consumption of 5-15 g/day of soluble fibre from oat product may be beneficial in reducing the CVD risk.⁽¹¹⁾ Health Authorities' approvals are based on a diet containing at least 3 g oat beta-glucan per day.⁽¹²⁾

Health Canada approval recognizes the relation between the increased oats (*Avena sativa*)-soluble fibre consumption and the reduction in total serum cholesterol level, and the reduction of the risk of CAD. The main active food component responsible for the hypocholesterolaemic property of oats is beta-glucan.^(9, 12)

Beta-glucan is a highly viscous soluble fibre composed of D-glucose monomers linked by a combination of β -(1 to 4) and β -(1 to 3) glycosidic bonds. It is thought that beta-glucan reduces TC and LDL-C by forming a viscous mass in the small intestine, thus limiting intestinal absorption of dietary cholesterol as well as the re-absorption of bile acids.⁽⁹⁾ In a randomized, single-blinded, controlled crossover study, it has been shown that gut microbiota were modulated in response to beta-glucan consumption on a molecular weight-dependent manner. The shift in gut microbiota might be one of the underlying mechanisms responsible for the physiological benefits of beta-glucan and this was correlated with reduced CVD risk factors.⁽¹³⁾

The EFSA Panel assumes that the target population is the general population and that the claimed effects refer to the maintenance of normal blood LDL-C concentrations, increasing in satiety which leads to a reduction in energy intake, reduction of post-prandial glycaemic response and improvement of the digestive function.⁽¹⁰⁾

A systematic review of 16 studies conducted by Q. Hou *et al.* has shown that oat intake reduced the concentrations of TC and LDL-C. It is thought that the cholesterol-lowering effect might be due to beta-glucan binding with bile acids which leads to decreased cholesterol absorption, increased expression of hepatic LDL-C receptor, and increased faecal bile acid excretion. The effect of beta-glucan on HDL-C has varied in those studies.

Hou *et al.* have also demonstrated that oat intake has a moderately beneficial effect on glycaemic control and lipid profile in patients with type 2 diabetes. The beneficial effect on blood lipids and glycaemia have been found to be linked to the increased viscosity of the food bolus, delayed gastric emptying, lengthened intestinal transit time, slowed absorption of nutrients especially carbohydrates, and enhanced satiety. The authors have also shown that the effects on health depend on the dosage, chemical structure, molecular weight, solubility and viscosity of the oat. No evidence has been found linking oat consumption and allergic reactions or disease; however, the authors recommend using pure oats without wheat contamination in wheat hypersensitive patients.⁽¹⁴⁾

CEAPRO's beta-glucan is a high-medium molecular weight soluble fibre obtained by a Pressurized Gas eXpanded® (PGX) method, which is a novel drying technique for processing water-soluble biopolymers. The use of high-medium molecular weight beta-glucan, obtained by the PGX method, for 12 weeks may significantly reduce the level of LDL-C and contribute to reducing the cardiovascular disease risk.

This phase II trial is indicated in the context of substantial scientific evidence on the cholesterol lowering effect of beta-glucan, the existence of a beta-glucan monograph published by Health Canada and the need to better delineate the effective dosage of the new formulation of CEAPRO's beta-glucan^{(15), (16)}.

